10.4.3. Special Reporting Situations

Safety events of interest on a sponsor study drug in an interventional study that may require expedited reporting or safety evaluation include, but are not limited to:

- Overdose of a sponsor study drug
- Suspected abuse/misuse of a sponsor study drug
- Accidental or occupational exposure to a sponsor study drug
- Medication error involving a sponsor product (with or without subject/patient exposure to the sponsor study drug, eg, name confusion)
- Exposure to a sponsor study drug from breastfeeding

Special reporting situations should be recorded in the CRF. Any special reporting situation that meets the criteria of a serious adverse event should be recorded on the serious adverse event page of the CRF.

Retinal abnormalities should be reported as adverse events or as serious adverse events if the severity is Grade 3 or higher. Instructions for assessing vision abnormalities during the study are provided in Section 8.3.5.

In addition, growth disorder (including accelerated bone growth and SCFE) and fractures in children and adolescents (≥ 6 to <18 years) is an adverse event of special interest for erdafitinib. Growth disorder-related and fracture-related AEs of Grade 3 or higher severity in children and adolescents, regardless of seriousness, will be reported to the sponsor within 24 hours.

10.4.4. Procedures

All Adverse Events

All adverse events, regardless of seriousness, severity, or presumed relationship to study drug, must be recorded using medical terminology in the source document and the CRF. Whenever possible, diagnoses should be given when signs and symptoms are due to a common etiology (eg, cough, runny nose, sneezing, sore throat, and head congestion should be reported as "upper respiratory infection"). Investigators must record in the CRF their opinion concerning the relationship of the adverse event to study therapy. All measures required for adverse event management must be recorded in the source document and reported according to sponsor instructions.

For all studies with an outpatient phase, including open-label studies, the subject must be provided with a "wallet (study) card" and instructed to carry this card with them for the duration of the study indicating the following:

- Study number
- Statement, in the local language(s), that the subject is participating in a clinical study
- Investigator's name and 24-hour contact telephone number
- Local sponsor's name and 24-hour contact telephone number (for medical personnel only)
- Site number
- Subject number
- Any other information that is required to do an emergency breaking of the blind

Serious Adverse Events

All serious adverse events that have not resolved by the end of the study, or that have not resolved upon discontinuation of the subject's participation in the study, must be followed until any of the following occurs:

- The event resolves
- The event stabilizes
- The event returns to baseline, if a baseline value/status is available
- The event can be attributed to agents other than the study drug or to factors unrelated to study conduct
- It becomes unlikely that any additional information can be obtained (subject or health care practitioner refusal to provide additional information, lost to follow-up after demonstration of due diligence with follow-up efforts)

Suspected transmission of an infectious agent by a medicinal product will be reported as a serious adverse event. Any event requiring hospitalization (or prolongation of hospitalization) that occurs

during the course of a subject's participation in a study must be reported as a serious adverse event, except hospitalizations for the following:

- Hospitalizations not intended to treat an acute illness or adverse event (eg, social reasons such as pending placement in long-term care facility)
- Surgery or procedure planned before entry into the study (must be documented in the CRF). Note: Hospitalizations that were planned before the signing of the ICF, and where the underlying condition for which the hospitalization was planned has not worsened, will not be considered serious adverse events. Any adverse event that results in a prolongation of the originally planned hospitalization is to be reported as a new serious adverse event.
- A standard procedure for protocol therapy administration will not be reported as a serious adverse event. (Hospitalization or prolonged hospitalization for a complication of therapy administration will be reported as a serious adverse event).
- Administration of blood or platelet transfusion. (Hospitalization or prolonged hospitalization for a complication of such transfusion remains a reportable serious adverse event.)
- Procedure for protocol/disease-related investigations (eg, surgery, scans, endoscopy, sampling for laboratory tests, bone marrow sampling) (Hospitalization or prolonged hospitalization for a complication of such procedures remains a reportable serious adverse event).
- Prolonged hospitalization for technical, practical, or social reasons, in absence of an adverse event.

Expected progression of disease should not be considered or reported as an AE (or SAE). However, if determined by the investigator to be more likely related to the study treatment than being expected from the underlying disease, the treatment-invoked progression (ie the treatment-invoked signs/symptoms of such progression) should be reported per the usual reporting requirements (refer to Adverse Event Definitions and Classifications in Section 10.4, Adverse Events: Definitions and Procedures for Recording, Evaluating, Follow-up, and Reporting).

Death that is attributed by the investigator explicitly to progression of disease should not be considered nor reported as an AE (or SAE). However, if determined by the investigator to be more likely related to the study treatment than being expected from the underlying disease, the treatment-invoked death due to progression should be reported per the usual reporting requirements (refer to Adverse Event Definitions and Classifications in Section 10.4: Adverse Events: Definitions and Procedures for Recording, Evaluating, Follow-up, and Reporting).

Progression of disease and death due to disease progression should be documented on the appropriate eCRF forms (eg, the Disease Progression form and the Death form).

Signs or symptoms of disease progression that are of clinical significance, such as spinal cord compression, vena cava superior syndrome, major vessel rupture, efflux obstruction or organ failure, should be documented on the appropriate eCRF forms (eg, the Clinical Progression form).

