8.4.5. Pregnancy

All initial reports of pregnancy in female subjects or partners of male subjects must be reported to the sponsor by the study-site personnel within 24 hours of their knowledge of the event using the appropriate pregnancy notification form. Abnormal pregnancy outcomes (eg, spontaneous abortion, fetal death, stillbirth, congenital anomalies, ectopic pregnancy) are considered serious adverse events and must be reported using the Serious Adverse Event Form. Any subject who becomes pregnant during the study must be promptly withdrawn from the study and discontinue further study drug. Follow-up information regarding the outcome of the pregnancy and any postnatal sequelae in the infant will be requested. Follow-up information may continue to be collected up to 12 months after the birth of a baby, if a congenital anomaly or significant medical condition is diagnosed at birth.

8.4.6. Disease-related Events and Disease-related Outcomes Not Qualifying as Adverse Events or Serious Adverse Events

All events that meet the definition of a SAE will be reported as SAEs, regardless of whether they are protocol-specific assessments.

Progression of disease should not be considered an AE (or SAE). However, signs and symptoms of disease progression or of clinical sequelae resulting from disease progression/lack of efficacy

that are determined by the investigator to be of clinical significance should be reported per the usual reporting requirements (Section 10.4).

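### Protocol Sections 8.4.6 and 10.4.4 set different triggers for reporting clinically significant complications of progression as AEs or SAEs, so all-cause serious and Grade 3 or worse TEAE counts can depend on which section a site follows

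*Protocol*

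**What the plan says.** Four provisions of the Protocol bear on a sign, symptom or complication of tumour progression.

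- **Section 8.4.6.** Progression itself is not an AE or SAE. The section then covers "signs and symptoms of disease progression or of clinical sequelae resulting from disease progression/lack of efficacy" and says that those "that are determined by the investigator to be of clinical significance should be reported per the usual reporting requirements (Section 10.4"). Cause plays no part. The same section says that every event meeting the SAE definition is reported as an SAE.
- **Section 10.4.4, text on progression.** "Expected progression of disease should not be considered or reported as an AE (or SAE"). The exception applies "if determined by the investigator to be more likely related to the study treatment than being expected from the underlying disease", and in that case "the treatment-invoked progression (ie the treatment-invoked signs/symptoms of such progression) should be reported per the usual reporting requirements".
- **Section 10.4.4, text on forms.** Clinically significant signs or symptoms of progression are listed by example, starting with spinal cord compression. The list ends: "efflux obstruction or organ failure, should be documented on the appropriate eCRF forms (eg, the Clinical Progression form"). No AE or SAE form is named.
- **Section 10.4.4, general rules.** All AEs are recorded regardless of their presumed relationship to the drug. Any event requiring hospitalization "during the course of a subject's participation in a study must be reported as a serious adverse event", apart from listed exceptions. Progression is not among them.

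On the analysis side, incidence and severity of AEs is a secondary endpoint (Protocol Section 3). SAP Section 6.1.1 tabulates serious TEAEs and Grade 3 or worse TEAEs. Protocol Section 9.4.7 includes all reported TEAEs. Neither document has a rule that adds or removes progression-related events in these tables.

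**The concern.** Section 8.4.6 turns on clinical significance. The progression text of Section 10.4.4 turns on causality. Section 8.4.6 refers the reader to Section 10.4 for the usual requirements, so a site that follows the reference arrives at the other trigger. A condition based on cause also sits badly with the rule in the same section that AEs are recorded whatever their relationship to the drug.

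Two things are at stake. First, the all-cause safety tables are built from what sites report. Treatment normally runs to progression (Section 8.1.2) and may continue beyond it (Section 8.2.2). The TEAE window runs to 30 days after the last dose unless subsequent therapy starts earlier (SAP Section 6.1.2). Complications of progression can therefore fall inside the window. Second, in the long-term extension only SAEs are reported and nothing is entered in the eCRF (Appendix 13). The Clinical Progression form is not available there, so a serious complication handled under the restrictive reading of Section 10.4.4 might be reported nowhere.

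**Working it through.** No published figure is involved, so the check is to run defined cases through the provisions.

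| Case | Section 8.4.6 | Section 10.4.4, progression and forms text | Section 10.4.4, general rules |
|---|---|---|---|
| A. Clinically significant complication due to the tumour, no SAE criterion met | AE | Exception not met; Clinical Progression form named | Recorded if it is an AE, regardless of relationship |
| B. As A, but requiring hospitalization | SAE | Exception not met; Clinical Progression form named | SAE; progression is not a listed exception |
| C. Sign or symptom judged more likely due to treatment | AE, or SAE if criteria are met | AE, or SAE if criteria are met | Same |
| D. Progression as a bare term | Not an AE | Not an AE | Not addressed |

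Cases C and D give no conflict. Cases A and B do.

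**Direction.** Compare Section 8.4.6 with the restrictive reading of the progression text in Section 10.4.4. Every clinically significant event reportable under the second is reportable under the first, and cases A and B are reportable under the first alone. The SAP counts subjects with at least one event, so for serious TEAEs, and likewise for Grade 3 or worse TEAEs:

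subjects counted under 8.4.6 − subjects counted under 10.4.4 = subjects whose only such event in the TEAE window is a complication of progression not attributed to treatment.

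This difference is zero or positive.

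**Size.** It needs two inputs: how often such complications occur in the window, and how often the same subjects have another serious or Grade 3 or worse event. The documents give neither. They also do not show how sites divide between the two readings. No estimate follows.

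**Drug-related counts.** Case C is reportable under every provision, so the drug-related tables should change little. The SAP percentages are of subjects, so drug-related incidence does not rise because other events go unreported.

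**The case against.** The strongest reply is that the sections can be read together. The bar in Section 10.4.4 is on expected progression, which matches Section 8.4.6. The sentence on treatment-invoked progression adds a reporting duty and does not say that other signs and symptoms are excluded. The Clinical Progression form is given only as an example, so completing it need not replace an AE record. For serious events most of the text points towards reporting: the SAE sentence in 8.4.6, the SAE definition in Section 10.4.1, which does not depend on cause, and the hospitalization rule in 10.4.4.

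Much of this stands. A reader might infer that Section 10.4.4 permits reporting *only* when the event is treatment-invoked. That word is not in the text. It is an inference from the rule-and-exception structure and from the absence of any AE form in the sentence on clinically significant symptoms. The provisions favouring SAE reporting also make wholesale loss of serious events less likely. What remains is that the additive reading is nowhere stated, and the passage that names these complications points to a different form.

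It is also fair to say that new protocol wording comes late for adults. Their extension phase begins with approval of Amendment 6, when clinical-database collection ends (Appendix 13).

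**Conclusion.** The inconsistency is real and should be resolved. Two sites can each follow the Protocol and record the same tumour complication differently, so all-cause serious and Grade 3 or worse TEAE counts can depend on the section used. Counts under 8.4.6 are equal or higher. This rests on the text alone and on SAP tables that take events as reported. The primary ORR analysis is unaffected.

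Two stronger conclusions are tempting and not supported. A reader might attach a percentage-point shift to the serious TEAE rate. Any such figure would rest on assumed event frequencies, and it would compare all sites under one rule with all sites under the other, which is not the mixed practice at issue. A reader might also infer that, without a control arm, the reporting difference cannot be told apart from the drug's effect. Investigators record relationship for each AE, drug-related TEAEs are tabulated separately, and entries on the Clinical Progression form during the main study remain in the eCRF.

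**What to change.** 1. **Protocol Sections 8.4.6 and 10.4.4.** Use one rule in both. State in 10.4.4 that the Clinical Progression form is additional to, and does not replace, AE/SAE reporting of clinically significant signs, symptoms and complications of progression. Keep the existing provisions for the bare term of disease progression, for death attributed to it, and for treatment-invoked death.
2. **Appendix 13.** Make clear that the same rule governs SAE reporting in the long-term extension, where no eCRF data are collected.
3. **SAP Section 6.1.** For adult data already collected, add a supportive listing or summary of Clinical Progression form entries in the TEAE window with no matching AE record, shown beside the serious and Grade 3 or worse TEAE tables. Define a match in advance, for example by subject, date and term. This shows how far the two readings diverged in practice.

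The cost is wording in two sections and one appendix, plus one listing. Reported all-cause AE rates may rise somewhat in data still being collected. The documents do not show the fields on the Clinical Progression form. If it holds no grade or seriousness, its entries can be shown beside the TEAE tables but not merged into them. A split of AE tables by attribution to progression is not proposed, because the only AE attribution that the documents describe is to study treatment.

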10.4.5. Contacting Sponsor Regarding Safety

The names (and corresponding telephone numbers) of the individuals who should be contacted regarding safety issues or questions regarding the study are listed in the Contact Information page(s), which will be provided as a separate document.

10.4.6. Product Quality Complaint Handling

A product quality complaint (PQC) is defined as any suspicion of a product defect related to manufacturing, labeling, or packaging, ie, any dissatisfaction relative to the identity, quality, durability, or reliability of a product, including its labeling or package integrity. A PQC may have an impact on the safety and efficacy of the product. Timely, accurate, and complete reporting and analysis of PQC information from studies are crucial for the protection of subjects, investigators, and the sponsor, and are mandated by regulatory agencies worldwide. The sponsor has established procedures in conformity with regulatory requirements worldwide to ensure appropriate reporting of PQC information; all studies conducted by the sponsor or its affiliates will be conducted in accordance with those procedures.

Procedures

All initial PQCs must be reported to the sponsor by the study-site personnel within 24 hours after being made aware of the event.

If the defect is combined with a serious adverse event, the study-site personnel must report the PQC to the sponsor according to the serious adverse event reporting timelines (refer to Section 8.4.1, Time Period and Frequency for Collecting Adverse Event and Serious Adverse Event Information). A sample of the suspected product should be maintained for further investigation if requested by the sponsor.

Contacting Sponsor Regarding Product Quality

The names (and corresponding telephone numbers) of the individuals who should be contacted regarding product quality issues are listed in the Contact Information page(s), which will be provided as a separate document.

10.5. Appendix 5: ECOG Performance Status Scale

Grade	ECOG Performance Status Grade
0	Fully active, able to carry on all pre-disease performance without restriction
1	Restricted in physically strenuous activity but ambulatory and able to carry out work of a light or sedentary nature, eg, light house work, office work
2	Ambulatory and capable of all selfcare but unable to carry out any work activities. Up and about more than 50% of waking hours
3	Capable of only limited selfcare, confined to bed or chair more than 50% of waking hours
4	Completely disabled. Cannot carry on any selfcare. Totally confined to bed or chair
5	Dead

Reference: Oken MM, Creech RH, Tormey DC, et al. Toxicity and response criteria of the Eastern Cooperative Oncology Group. Am J Clin Oncol. 1982;596):649-655.

10.6. Appendix 6: ECOG/Karnofsky/Lansky Performance Scales

The Karnofsky Scale is designed for those aged 16 years and older. The Lansky Scale is designed for those less than 16 years of age.

ECOG	(Zubrod)	Karno	fsky	Lansky			
Score	Description	Score Description		Score	Description		
7.1	Fully active, able to carry on all pre-disease	100	Normal, no complaints, no evidence of disease.	100	Fully active, normal.		
0	on all pre-disease performance without restriction.	90	Able to carry on normal activity, minor signs or symptoms of disease.	90	Minor restrictions in physically strenuous activity.		
	Restricted in physically strenuous activity but	80	Normal activity with effort, some signs or symptoms of disease.	80	Active, but tires more quickly.		
1	ambulatory and able to carry out work of a light or sedentary nature, e.g., light housework, office work.	70	Cares for self, unable to carry on normal activity or do active work.	70	Both greater restriction of, and less time spent in, play activity.		
	Ambulatory and capable of all selfcare but unable to carry out any work activities. Up and about more than 50% of waking hours.	60	Requires occasional assistance, but is able to care for most of his/her needs.	60	Up and around, but minimal active play; keeps busy with quieter activities.		
2		50	Requires considerable assistance and frequent medical care.	50	Gets dressed, but lies around much of the day; no active play; able to participate in all quiet pla and activities.		
•	Capable of only limited selfcare, confined to bed or chair more than 50% of waking hours.	40	Disabled, requires special care and assistance.	40	Mostly in bed, participates in quiet activities.		
3		30	Severely disabled, hospitalization indicated. Death not imminent.	30	In bed, needs assistance even for quiet play.		
4	Completely disabled. Cannot carry on any	20	Very sick, hospitalization indicated. Death not imminent.	20	Often sleeping, play entirely limited to very passive activities.		
4	selfcare. Totally confined to a bed or chair.	10	Moribund, fatal processes progressing rapidly.	10	No play, does not get out of bed		
5	Dead	0	Dead	0	Dead		

The Karnofsky (Karnofsky 1948) and Lansky (Lansky 1987) Performance Scales with adaptation by the National Marrow Donor Program[®] and The Medical College of Wisconsin.


Source: Lansky et. al: Toward the Development of a Play Performance (PPSC), Cancer; 56: 1837-1840. Copyright © 1985 American Cancer Society. Reproduced with permission of John Wiley & Sons, Inc.

10.7. Appendix 7: Cockcroft-Gault (Adults) and CKiD Schwartz (Children [≥6 to <12 years] and Adolescents [≥12 to <18 years]) Formulas for Estimated Creatinine Clearance

Cockcroft-Gault Formula for Estimated Creatinine Clearance for Adults

eCR = (140-Age) x Mass (Kilograms) x [0.85 if female] 72 x Serum Creatinine (in mg/dL¹)

OR

eCcr = (140-Age) x Mass (Kilograms) x Constant Serum Creatinine (in µmol/L)

Where Constant = 1.23 for men and 1.04 for women

Reference: http://www.mdcalc.com/creatinine-clearance-cockcroft-gault-equation/

CKiD^a Schwartz Formula for Estimated Creatinine Clearance for Children (≥6 to <12 years) and Adolescents (≥12 to <18 years)

GFR (ml/min per 1.73 m(2)) =39.1[height (m)/Scr (mg/dl)](0.516) x [1.8/cystatin C (mg/L)](0.294)[30/BUN (mg/dl)](0.169)[1.099](male)[height (m)/1.4](0.188)

Reference: Schwartz GJ, Munoz A, Schneider MF, et al. New equations to estimate GFR in children with CKD. J Am Soc Nephrol. 2009;20:629-637.

^aCKiD=Chronic Kidney Disease in Children

10.8. Appendix 8: The Stages of Heart Failure – New York Heart Association (NYHA) Classification

Class	Patient Symptoms
Class I (Mild)	No limitation of physical activity. Ordinary physical activity does not cause undue fatigue, palpitation, or dyspnea (shortness of breath)
Class II (Mild)	Slight limitation of physical activity. Comfortable at rest, but ordinary physical activity results in fatigue, palpitation, or dyspnea.
Class III (Moderate)	Marked limitation of physical activity. Comfortable at rest, but less than ordinary activity causes fatigue, palpitation, or dyspnea.
Class IV (Severe)	Unable to carry out any physical activity without discomfort. Symptoms of cardiac insufficiency at rest. If any physical activity is undertaken, discomfort is increased.

Reference: Heart Failure Society of America The Stages of Heart Failure – NYHA Classification. Available at http://www.abouthf.org/questions_stages.html. Accessed October 6, 2008.

